Clinical study protocol
Programme No.: ajsfmtxy001

The effect of amino acid peritoneal dialysis fluid on the nutritional status of patients with maintenance peritoneal dialysis was investigated

Efficacy and safety: a multicenter, open, prospective, self-controlled clinical trial research

Peritoneal dialysis Center, Gaozhou People's Hospital

Programme date: 30 September 2023
Version number: 1.0

Confidentiality statement

The content included in this document, especially unpublished data, is owned by the Gaoyang People's Hospital Peritoneal Dialysis Center. It is provided to you under confidentiality for review by the Ethics Committee/Institutional Review Board. Please remember that, except when necessary to obtain informed consent from patients who may receive trial treatments, the content of this document must not be disclosed to any other person or entity without written approval from our institution.

scenario summary

title	To explore the effectiveness of amino acid peritoneal dialysis fluid in improving the nutritional status of patients undergoing maintenance peritoneal dialysis and safety: a multicenter, open, prospective, self-controlled clinical study
Applicant	Peritoneal dialysis Center, Gaozhou People's Hospital
purpose of research	To explore the effectiveness and safety of amino acid peritoneal dialysis fluid on the nutritional status of peritoneal dialysis patients performance assessment
research design	Multicenter, open, prospective, self-controlled study
Study duration	Each subject will be studied for six months, and the entire study will be completed in about a year.
Number of researchers	140 patients with malnutrition were selected for peritoneal dialysis
Center number	Five centres are expected
Main research unit	Peritoneal dialysis Center, Gaozhou People's Hospital
Criteria for inclusion	
1. Patients with malnutrition in uremia were screened and maintained peritoneal dialysis for at least 3 months. The criteria for malnutrition should meet at least 2 of the following items:(1) serum albumin level <3.5g/dL (35g/L), (2) prealbumin <300mg/L, (3) modified Good Law Subjective Comprehensive Nutritional Assessment (Subjective Global Assessment, SGA)> 7 points;2. Blood urea nitrogen less than or equal to 38mmol/L;3. The patient's age is between 18 and 75;4. The patient signs the informed consent form.

	
1. Allergy to any amino acid or excipient in this product;
 
2. Have had peritonitis more than once in the last 3 months; have had peritonitis in the last 1 month inflammation or hospitalization;
 
3. Combine hyperthyroidism, systemic infection fever and other high metabolic state diseases, as well as taking medication drugs that affect tissue metabolism, such as corticosteroids;
 
4. Congenital amino acid metabolic defects, acute severe pancreatitis, severe hyperbilirubinemia
 
5. Malignant tumor metastasis or diffusion, residual cancer after treatment, coagulation dysfunction, regeneration patients with obstructive anemia, severe diseases of other systems such as heart, brain and lung;
 
6. Kidney transplant may be accepted during the trial;
 
7. Active hepatitis B or C, cirrhosis, active liver disease, liver dysfunction or human immunodeficiency virus (HIV) serum reaction positive;
 
8. Participants who have participated in other drug clinical trials within 3 months before enrollment;
 
9. Pregnant and lactating women;
 
10. The mental state cannot cooperate;
 
11. No written informed consent has been signed;
 
12. Unable or unwilling to comply with the protocol approved by the investigator;

--	---

The patient withdrew	
Participants can withdraw from the study under any circumstances and should do so in the following situations withdrawal studies:
 
(1) The patient develops life-threatening complications;(2) The occurrence of intolerable clinical symptoms related to the therapeutic drug;(3) Pregnancy was combined during the study;(4) Violation of the test plan;(5) Unwilling to continue participation in the study;(6) Disappearance.
Study treatment	Each subject received a daily dose of 1 bag of amino acids for 6 months plus 2-4 daily treatment with bagged glucose peritoneal dialysis fluid.
Research process	
Each subject received a 6-month treatment of 1 bag of amino acid peritoneal dialysis and 2-4 bags of glucose peritoneal dialysis fluid per day (the amount of glucose peritoneal dialysis fluid was determined according to the treatment protocol at screening when the patient entered the study). Before and during treatment, in the 1st, 3rd and 6th months, the subjects were evaluated for various efficacy and safety indicators
 
Estimate and record any adverse events or serious adverse events. Follow up monthly during treatment assess subjective feelings (infusion pain, abdominal distension), blood pressure, weight, urine volume, and ultrafiltration.

Endpoint of efficacy	Efficacy indicators: serum albumin, prealbumin and body mass, body mass index (Body mass index, BMI), lean body mass index (con icity index, CI), waist circumference and grip strength, upper arm muscle circumference, standardized protein catabolic rate (Normalized protein catabolic rate, nPCR), standardized protein total nitrogen excretion rate (Normalized protein nitrogen appearance,nPNA). Glycated hemoglobin, fasting blood glucose, Nt-pro BNP, weekly urea clearance index (Kt/V), weekly creatinine clearance (Ccr), and oral glucose tolerance test (peritoneal equilibration test, PET)
Security assessment	Safety indicators: patient blood pressure, ultrafiltration volume, urine volume, Nt-pro BNP, Kt/V, Ccr, PET, adverse event monitoring.

statistical analysis	
analytic set
 
Full analysis set (Full Analysis Set, FAS): All with at least one exposure subjects studied for treatment. This analysis set will be used primarily for the analysis of baseline data. Set of Safety Analyses (Safety Analysis Set, SS): At least one study was accepted all subjects treated and with a record of safety after medication. Effectiveness Analysis Set (Effectiveness Analysis Set, EAS): All subjects included received at least one study treatment and had at least one post-treatment observation subjects for the evaluation of the effectiveness of the intermediate point.
 
statistical analysis technique
 
Continuous variables will be statistically described according to the data distribution, including number of cases (non-missing), mean, standard deviation, median and quartiles, maximum and minimum values.
 
Calculate the number and percentage of each category of categorical variables.
 
Main endpoint: Descriptive analysis was used to summarize baseline, post-treatment 6 months albumin and prealbumin measurements, and the difference in change from baseline of enrolled subjects. Paired t-tests were used to test for differences before and after treatment, and multiple problems were controlled by Hochberg method.
 
Secondary endpoints: Descriptive analysis will be used to summarize the baseline, three months post-treatment, and six months post-treatment nutritional status, metabolic status, residual renal function, and trends in dialysis adequacy for enrolled subjects, with graphical presentations;
 
Tests for changes relative to baseline: For continuous variables, paired t-tests or Wilcoxon's signed-rank test will be used to compare pre-and post-treatment differences based on data distribution; for categorical

----------------------	---

	
variables, McNemar-tests will be used to compare the behavior before and after.
 
Safety analysis: Descriptive statistics were used to summarize adverse events and adverse reactions, drug-related treatment measures, outcomes, and severity classification. Subgroups were used if necessary(For example, whether dialysis is adequate or heart failure) stratified analysis of data was performed.
 
Exploratory analysis: patients were divided into adequate and inadequate groups according to baseline $Kt/V \geq 1.7$. The improvement of nutritional indicators in different subgroups was analyzed.

--	--

catalogue

Peritoneal dialysis is a treatment method that uses the peritoneum as a semipermeable membrane. By injecting dialysate into the abdominal cavity, metabolic waste and excess water in the blood are allowed to permeate and diffuse into the dialysate, which is then drained from the body. This process helps remove toxins from the body and regulate electrolyte balance. Peritoneal dialysis has several advantages, including ease of operation, no need for an intravenous access, minimal impact on hemodynamics, the ability to preserve residual kidney function, and the flexibility to control treatment time and location. It is widely used as a substitute for kidney therapy in patients with end-stage chronic renal failure method.

However, long-term peritoneal dialysis can also lead to some adverse consequences, one of which is malnutrition. Malnutrition refers to a state where the nutrients ingested or absorbed by the body cannot meet its physiological needs, leading to dysregulation in the body's composition, function, or metabolism. Malnutrition is very common among patients undergoing maintenance peritoneal dialysis, with an incidence rate as high as 20% to 70%. The causes of malnutrition are numerous, including metabolic disorders due to reduced kidney function, decreased appetite, gastrointestinal symptoms, restricted diets, and medication use. Additionally, peritoneal dialysis itself can exacerbate the development of malnutrition its development is mainly manifested in: loss of proteins and amino acids: about 5 to 15g of protein is excreted daily through peritoneal dialysis fluid, of which about half is albumin. At the same time, about 10 to 20g of free amino acids are lost daily. These proteins and the loss of amino acids leads to negative nitrogen balance and decreased serum albumin levels.

Glucose absorption: Conventional peritoneal dialysis fluids contain high concentrations of glucose as a osmotic agent to increase the amount of water filtered. However, these glucose are also absorbed by the body, about 80-120g per day. These additional energy intake can lead to metabolic disorders such as obesity, hyperinsulinemia, insulin resistance and diabetes.

Inflammatory response: long-term peritoneal dialysis will cause chronic micro-inflammatory response, resulting in increased catabolic metabolism, reduced synthetic metabolism, decreased appetite, endocrine dysfunction and so on. At the same time, inflammatory response will also affect vascular permeability and hemodynamics, reducing ultrafiltration efficiency and the ability to remove toxins.

Malnutrition not only affects the quality of life of peritoneal dialysis patients, but also increases the risk of complications such as infection, cardiovascular events, and peritoneal failure, reducing survival rates. Therefore, improving the nutritional status of peritoneal dialysis patients,

It is one of the important measures to improve its prognosis and quality of life.

Currently, nutritional support strategies for peritoneal dialysis patients mainly include oral nutritional supplementation, enteral nutrition supplementation, parenteral nutrition supplementation, and modified peritoneal dialysate. Among these, modified peritoneal dialysate refers to adding beneficial components such as amino acids, ketones, and low-osmolarity agents to conventional glucose-containing peritoneal dialysate. This reduces glucose absorption, increases the clearance of water and toxins, provides essential amino acids and energy, and improves the body's metabolic function

Check your physical and nutritional status.

Amino acids are the fundamental units for protein synthesis and other important substances in the body, and they also serve as one of the key energy sources for oxidative metabolism. Amino acid peritoneal dialysate is a sugar-free and osmotic agent-free peritoneal dialysate containing 1.1% (11 g/L) free amino acids, with an amino acid composition similar to that found in human plasma. The main mechanisms of action of Amino acid peritoneal dialysis fluid are as follows: supplemental amino acids: Amino acid peritoneal dialysis fluid can provide amino acids to the blood through peritoneal diffusion, thus to compensate for the loss of protein and amino acids, increase serum albumin level, improve the body nitrogen balance and nutritional status.

Providing Energy: Amino acid peritoneal dialysate can serve as a sugar-free osmotic agent, moving water from the blood to the dialysate through osmotic pressure differences, thus achieving ultrafiltration. At the same time, amino acids can be absorbed by the body and participate in energy metabolism, providing about 40kcal of energy daily. This not only reduces the need for high-concentration glucose. Sugar dependence can also avoid the metabolic disorder caused by excessive absorption of glucose.

Metabolic Regulation: Amino acid peritoneal dialysis fluid can influence the secretion and activity of various hormones and cytokines in the body, thereby regulating metabolism. For example, amino acids can stimulate the secretion of insulin, glucagon, growth hormone, and insulin-like growth factor-1, promoting glucose utilization and protein synthesis; amino acids can also inhibit the secretion of tumor necrosis factor- α and interleukin-6, etc., inhibits inflammatory response and protein breakdown.

Amino acid peritoneal dialysate, as an improved version of peritoneal dialysate, has been clinically applied and studied in many countries and regions both domestically and internationally. Currently, numerous studies have confirmed the beneficial effects of amino acid peritoneal dialysate on the nutritional status of patients undergoing maintenance peritoneal dialysis [1-10]. For example, Sun Bin [1] et al. investigated the impact of amino acid peritoneal dialysis on the dialysis efficiency and nutritional status of peritoneal dialysis patients. The results showed that amino acid peritoneal dialysis can increase serum albumin levels, reduce urea nitrogen, uric acid, and blood phosphorus levels, and elevate hemoglobin levels, thereby improving the nutritional status of patients. Sun Yuling[3] et al. compared the effects of amino acid peritoneal dialysate and traditional glucose peritoneal dialysate on peritoneal mesothelial cells, finding that amino acid peritoneal dialysate better maintains cell viability, adhesion function, and protein synthesis. Faller[6] et al. treated peritoneal dialysis patients with optimized 1.1% amino acid peritoneal dialysate for 3 months and observed significant increases in serum albumin and transferrin levels. Jones [7] et al. found that compared to glucose dialysate, amino acid dialysate can improve albumin, prealbumin, and transferrin levels in malnourished peritoneal dialysis patients, and also observed improvements in muscle nutrition indicators. Delarue[9] et al. studied the impact of amino acid dialysate on creatine metabolism and found that amino acid dialysate can stimulate creatine release and increase protein synthesis. Li[10] et al. conducted a 3-year randomized controlled study, and the results showed that long-term use of amino acid dialysate can improve the nutritional status of peritoneal dialysis patients, especially for female patients. The above studies show that amino acid peritoneal dialysis fluid can effectively improve the nutrition of patients with maintenance peritoneal dialysis.

The state of temperament and metabolism promotes its growth and development and physical improvement. However, a meta-analysis in 2021 [13] comprised a review of 6,945 abstracts, including 14 studies (9 randomized and 5 non-randomized), concluded that amino acid peritoneal dialysate may not alter anthropometric indicators, the impact on serum albumin is uncertain, and the estimated differences are unlikely to have clinical significance. However, due to the low quality of evidence, these findings should be interpreted with caution. Based on the above meta-analysis, robust research is needed to address the limitations in the evidence. Therefore, we propose a multicenter, open, prospective, self-controlled clinical study aimed at observing the effects of amino acid

peritoneal dialysate on the nutritional status of patients undergoing maintenance peritoneal dialysis, as well as its safety assessment, with a view to promoting its clinical application

The application provides stronger evidence. The characteristics of this study are as follows:

Multicenter: This study will be conducted in five different regions of Guangdong province to improve the study its universality and representativeness.

Open: This study will not have a placebo or control group, but will use a self-control design, that is, each subject will be compared with the observation indicators before and after receiving amino acid peritoneal dialysis treatment to reduce individual differences and the influence of interfering factors.

Prospective: A detailed study protocol will be developed before the formal start of the study and will be carried out in accordance with the protocol. Record, report and other work to ensure the quality and credibility of the research.

Self-control: This study will use a self-control design, that is, each subject will receive amino acid peritoneal dialysis. The comparison of observation indicators before and after exudation therapy was carried out to reduce the influence of individual differences and other interfering factors.

2. Research objectives

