3.1 Research design

This study adopts a multicenter, open, prospective, and self-controlled design, where each participant serves as their own control before and after receiving amino acid peritoneal dialysis fluid treatment, to compare changes in their nutritional status. This study does not set up a placebo or control group, as amino acid peritoneal dialysis fluid is already on the market, with its efficacy and safety proven, and there are no equivalent alternatives. The primary objective of this study is to observe the nutritional improvement effects and safety assessment of amino acid peritoneal dialysis fluid for malnourished peritoneal dialysis patients. Specific techniques

The route is shown in Figure 1:

[figure not shown]

Figure 1. Technical route

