3.3.1 Selection criteria

1. Select patients with uremia with malnutrition during the screening period and maintain peritoneal dialysis for at least 3 months. Malnutrition

The standard shall at least meet two of the following items:

(1) Serum albumin level <3.5g/dL (35g/L),

(2) Prealbumin <300mg/L,

(3) Subjective comprehensive nutritional assessment (SGA)> 7 points;

2. Blood urea nitrogen \leq 38mmol/L;

3. The patient is between 18 and 75 years of age;

4. The patient signs an informed consent form.

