7.6.2 Statistical analysis of the primary endpoint

Statistical analysis of the primary endpoint will be based on the EAS set, including primary analysis and sensitivity analysis.

1) Main analysis:

1) Descriptive analysis will be used to summarize the baseline, post-treatment 6 months albumin and pre-protein measurements of the subjects in the group, as well as the difference in change from baseline; LOCF will be used to process the data on major efficacy loss

The paired t-test was used to test the difference before and after treatment.

2) Sensitivity analysis: The robustness of the analysis results will be evaluated by considering different missing data processing situations. The missing data of the main efficacy after treatment will be filled with the mean and median of the complete observation data respectively method, hypothesis testing is the same as the main analysis.

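### The plan takes zero change from one baseline value as the course without the fluid and calls a significant change effective; a single-arm comparison cannot support that attribution, and the bias could run either way.

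*Combined protocol and SAP*

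**What the plan says.** - **Design claim.** Section 1, under the Open and Self-control features, says patients are compared "before and after receiving amino acid peritoneal dialysis treatment to reduce individual differences and the influence of interfering factors".
- **Reason for no control.** Section 3.1 justifies the absence of a control arm by the product's marketed status, and describes the product as one "with its efficacy and safety proven, and there are no equivalent alternatives". Section 1 nevertheless reports a 2021 meta-analysis from which "the impact on serum albumin is uncertain", and concludes that robust research is needed.
- **Course on dialysis.** Section 1 says of losses into the dialysis fluid that "the loss of amino acids leads to negative nitrogen balance and decreased serum albumin levels". It gives no rate.
- **Test.** Section 7.6.2: "The paired t-test was used to test the difference before and after treatment". The null value is therefore zero mean change. Sections 7.1 and 7.7 make the test one-sided.
- **Success rule.** Sections 3.2.1, 7.1 and 7.7 call the treatment effective if the change in either albumin or prealbumin is significant.
- **Time before treatment.** Section 3.3.1 requires patients to "maintain peritoneal dialysis for at least 3 months". Section 7.3 says every subject first has three months on conventional fluid and describes this as part of the self-control design. Section 4.1 has only a screening and a treatment phase. Its Table 1 schedules albumin and prealbumin at screening, month 3 and month 6. Section 7.6.2 uses no earlier period.

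**The concern.** Using each patient as their own control cancels what is fixed about that patient. It does not cancel what would have happened to the same patient over the next six months anyway, nor anything else that changes after baseline. The plan allows such changes: dietary management under the researcher's guidance (section 4.1) and nutritional support and education when markers fall (section 5.1.2).

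The paired test credits all movement away from zero to the fluid. That is valid only if untreated albumin and prealbumin would on average have stayed flat. No section argues for this, and the loss mechanism in section 1 gives a reason to doubt it. Entry on low albumin or low prealbumin (section 3.3.1) pushes the other way, because values selected for being low tend to be higher when repeated.

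At stake is the meaning of the headline result. Section 1 presents the study as a source of stronger evidence for clinical use, and the success rule turns a change from baseline into a statement of efficacy. A reader could not tell fluid effect, natural course and co-intervention apart.

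**Working it through.** **Inputs.** From section 7.1: albumin expected to go from 27 to 28.5 g/L (difference 1.5), SD 4.5; prealbumin from 240 to 300 mg/L (difference 60), SD 80; one-sided level 0.0125; power 0.90; 112 evaluable patients. From section 7.7: one-sided levels 0.025 and 0.0125 for the two Hochberg steps. The documents give no untreated rate of change, so **every drift value below is an assumption**.

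**Step 1: reproduce the plan's figures.** n = [(z(0.9875) + z(0.90)) × SD / difference]², with z values 2.2414 and 1.2816.
- Albumin: (3.5230 × 4.5 / 1.5)² = 111.7, so 112.
- Prealbumin: (3.5230 × 80 / 60)² = 22.06, so 23.
- Dropout: 112 / 0.80 = 140.

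All three agree with the plan. The formula as printed lacks the square on the sum of z values, but the stated figures come from the squared form.

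**Step 2: the smallest significant albumin change.** The standard error is 4.5 / √112 = 0.425 g/L. The one-sided 0.0125 critical t on 111 degrees of freedom is 2.272. The observed mean change must exceed 2.272 × 0.425 = 0.97 g/L.

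**Step 3: albumin test under assumed drift.** Mean change = fluid effect + untreated drift. The probability of significance comes from the noncentral t with noncentrality (mean change) / 0.425.

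| Fluid effect over untreated course (g/L) | Assumed six-month drift (g/L) | Mean change (g/L) | P(albumin significant) |
|---|---|---|---|
| 1.5 | 0 | 1.5 | 0.89 |
| 1.5 | -0.25 | 1.25 | 0.75 |
| 1.5 | -0.5 | 1.0 | 0.53 |
| 1.5 | -1.0 | 0.5 | 0.14 |
| 0 | 0 | 0 | 0.0125 |
| 0 | +0.5 | 0.5 | 0.14 |
| 0 | +1.0 | 1.0 | 0.53 |

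The first row is slightly below 0.90 because the plan's formula uses the normal distribution.

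**Step 4: the either/or rule.** With n = 112 and SD 80, the standard error for prealbumin is 80 / √112 = 7.56 mg/L. At one-sided 0.0125, the prealbumin test alone is significant about 65% of the time for a mean change of +20 mg/L, 95% for +30, and almost always for the planned +60. So trial success does not depend on albumin. This does not help attribution, because prealbumin is also compared with zero.

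**Step 5: an upward influence of plausible size.** Assume albumin in the source population has mean 30 to 35 g/L and SD 4.5, selection is on a value below 35, and the test-retest correlation is 0.5 to 0.9. Regression to the mean alone then gives about +0.1 to +1.8 g/L. The entry rule needs two of three criteria, so this is only a rough guide. It shows that upward bias comparable to the planned 1.5 g/L cannot be excluded.

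**The case against.** Several points on the other side stand.

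- **Trial-level failure does not follow.** A reader might infer that a fluid which merely halts a decline would be scored as ineffective. The success rule does not support that: prealbumin alone can carry the trial (step 4). The inference holds for the albumin test, or if both markers stay flat.
- **The background does not forecast a fall.** A reader might take section 1 to say that albumin keeps dropping on conventional fluid. It describes a mechanism attributed to peritoneal dialysis itself. It gives neither a rate nor a six-month trend for patients already on dialysis for at least three months.
- **The lower figures in step 3 are not the plan's power.** Section 7.1 defines 1.5 g/L as the observed change, 28.5 minus 27, which already includes any drift. Step 3 treats 1.5 g/L as benefit over the untreated course, a different estimand, and adds assumed drift.
- **The stated aim is improvement.** Not counting stabilisation as success is consistent with sections 2.1 and 3.2.1.
- **The design claim is partly true.** Section 1 speaks of reducing interfering factors, and removing stable patient differences does reduce some. Section 5.2 also bars adding nutritional drugs after entry, which limits one co-intervention.

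None of this supplies a reason to treat zero as the untreated course, or resolves the conflict between sections 1 and 3.1.

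**Conclusion.** The concern holds in a limited form. The plan shows change from baseline and labels it efficacy. Zero change is an unsupported reference for both primary markers, and the bias may run either way.

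For albumin, an assumed drift of 1.0 g/L, two-thirds of the planned 1.5, is enough to mislead. If upward, it makes an inert fluid significant about 53% of the time; if downward, it cuts detection of a 1.5 g/L benefit to about 14%. These figures rest on the planning SD, 112 evaluable patients and drift values that the documents do not supply. They show sensitivity and do not estimate the bias.

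The documents do not support a claim that the trial is biased against the fluid, or that it would fail if the fluid only stabilised albumin.

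Two contradictions stand without any drift assumption: efficacy already proven (section 3.1) against an uncertain albumin effect (section 1), and the three-month conventional-fluid period of section 7.3 against a schedule and analysis that contain no such period.

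**What to change.** 1. **Limit the conclusion.** In sections 3.2.1, 7.1 and 7.7, replace the statement that treatment is effective with one that there is a significant change from baseline. State that the design alone cannot attribute this change to the fluid.
2. **Reconcile sections 1 and 3.1.** Efficacy cannot be proven in one and the albumin effect uncertain in the other. Confine the section 1 claim to reducing stable differences between patients.
3. **Reconcile section 7.3 with sections 4.1 and 7.6.2.** State whether the conventional-fluid period is part of the study or only prior history, and whether albumin and prealbumin are measured in it.
4. **Add a supportive analysis to section 7.6.2.** Where values from that period or from routine records exist, compare mean change before the fluid with mean change during it. Leave out the qualifying screening value and report the difference with a 95% confidence interval. Say how many patients contribute.

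**Cost.** Items 1 to 3 are wording. Item 4 needs chart abstraction, with no new patients, visits or samples. The documents do not show that earlier values exist. They may be sparse and irregular, particularly for prealbumin and for patients near the three-month minimum, and only two on-treatment measurements are scheduled. The analysis can therefore be supportive only, and attribution should not be made to rest on it.
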